1.2 Test Hypotheses

This proposal will test the primary hypothesis that:

- A. The magnitude of the reduction in corneal epithelial surface cell exfoliation following wear of the new DAILIES TOTAL1 water gradient lens will be less than the magnitude of the reduction measured following wear of a control, high oxygen permeable silicone hydrogel daily disposable contact lens.

This proposal will test the secondary hypothesis that:

[figure not shown]
- A. The area of corneal surface epithelial cells will not be increased over baseline following wear of the new DAILIES TOTAL1 water gradient lens while the area of corneal surface epithelial cells will be increased following wear of a control, high oxygen permeable silicone hydrogel daily disposable contact lens.

This proposal will test the following exploratory hypotheses:

- A. There will be an improvement in the biology of the lid wiper region following wear of the new DAILIES TOTAL1 water gradient lens when compared to a control, high oxygen permeable silicone hydrogel daily disposable contact lens.
- B. Surface area of limbal epithelial cells will be unchanged following wear of the new DAILIES TOTAL1 water gradient lens, whereas area will be increased following wear of a control, high oxygen permeable silicone hydrogel daily disposable contact lens.

- C. Limbal and central epithelial thickness will be unchanged following wear of the new DAILIES TOTAL1 water gradient lens, whereas thickness will be reduced following wear of a control, high oxygen permeable silicone hydrogel daily disposable contact lens.
- D. Dendritic cell infiltration in the limbal region will be unchanged following wear of the new DAILIES TOTAL1 water gradient lens, whereas dendritic cell infiltration will be increased following wear of a control, high oxygen permeable silicone hydrogel daily disposable contact lens.
- E. Extracellular DNA content of tear fluid will be unchanged following wear of the new DAILIES TOTAL1 water gradient lens, whereas DNA content will be increased following wear of a control, high oxygen permeable silicone hydrogel daily disposable contact lens.

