1.3 Protocol Overview

2.0 SPECIFIC OBJECTIVES

1. The primary experimental objective of this study is to characterize the effect of the DAILIES TOTAL1 compared to a control, high oxygen permeable silicone hydrogel daily disposable contact lens, the ACUVUE TruEye, on corneal epithelial cell desquamation. This effect will be assessed using a standardized ocular irrigation technique to measure:
 - a. Rate of desquamation of corneal epithelial cells (cells/min).
2. The secondary experimental objective of this study is to evaluate the effect of wear of the DAILIES TOTAL1 on the central corneal epithelium compared to a control, high oxygen permeable silicone hydrogel daily disposable contact lens, the ACUVUE TruEye. This effect will be assessed using IVCN to measure:
 - a. Area of surface epithelial cells within the central cornea (μm^2).
3. Multiple exploratory aims will also be investigated. These aims will be used to evaluate the effects of lens wear on the biology of the corneal and limbal epithelium, lid wiper and changes in the extracellular tear content of DNA in response to wear of the DAILIES TOTAL1 compared to a control, high oxygen permeable silicone hydrogel daily disposable contact lens, the ACUVUE TruEye. These will be assessed by:
 - a. Area of surface epithelial cells within the limbal region.
 - b. Dendritic cell infiltration in the limbal region.
 - c. Staining of the lid wiper region with sodium fluorescein and lissamine green.
 - d. IVCN evaluation of the eyelid.
 - e. Quantification of extracellular DNA adherent to the posterior lens surface and in the post lens tear film.

Detailed descriptions of the study design, procedures, data management and human protection are provided in the following sections.

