3.2 Study Workflow

Visit 1: Comprehensive ocular examination (Contact Lens Clinic at UTSW)

- a. Informed consent reviewed and signed
- b. Comprehensive examination
- c. Back-up glasses ordered as needed
- d. Lens fitting and ordering based on randomization into the following lens groups:
 - i. Alcon DAILIES TOTAL1
 - ii. Johnson and Johnson ACUVUE TruEye
- e. One month washout begins immediately or after the participant obtains the spectacles.

Visit 2: Baseline Visit, lens 1 dispensed (+/- 3 days)

- a. Brief screening exam
- b. Informed consent re-reviewed
- c. Baseline biological indicators (outcome measures) assessed
 - i. Tear collection OU
 - ii. Lid wiper staining OD
 - iii. Ocular irrigation OS
 - iv. Confocal microscopy of cornea, limbus and lid margin OD
- d. Lenses dispensed

Visit 3: 1 week of lens wear (+/- 3 days)

- a. Contact lens check up
 1. Snellen Visual Acuity Testing
 2. Lens fitting
 3. Slit lamp examination without corneal staining

Visit 4: 2 month of lens wear (+/- 3 days)

- a. Brief screening exam
- b. Lenses and diaries collected
- c. Biological indicators assessed
 - i. Lenses collected OU
 - ii. Tear collection OU
 - iii. Lid wiper staining OD
 - iv. Ocular irrigation OS
 - v. Confocal microscopy of cornea, limbus and lid margin OD
- d. Patient begins next 1 month washout period

Visit 5: Baseline visit, lens 2 dispensed (+/- 3 days)

- a. Brief screening exam
- b. Baseline biological indicators assessed
 - i. Lenses collected OU
 - ii. Tear collection OU
 - iii. Lid wiper staining OD
 - iv. Ocular irrigation OS
 - v. Confocal microscopy of cornea, limbus and lid margin OD
- c. Lenses dispensed – begin crossover phase

Visit 6: 1 week of lens wear (+/- 3 days)

- a. Contact lens check up
 - i. Snellen Visual Acuity Testing
 - ii. Lens fitting
 - iii. Slit lamp examination without corneal staining

Visit 7: 2 month of lens wear (+/- 3 days)

- a. Brief screening exam
- b. Lenses and diaries collected
- c. Biological indicators assessed
 - i. Lenses collected OU
 - ii. Tear collection OU
 - iii. Lid wiper staining OD
 - iv. Ocular irrigation OS
 - v. Confocal microscopy of cornea, limbus and lid margin OD
- d. Study completed

Table 1: Overall study design

Visit No.	Interval	Time in lens	Procedures
1	0	0	Sign and review IC. Comprehensive ocular examination. Order back-up glasses if needed. Lens fitting and ordering. One month washout period of no lens wear.

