3.4.4 Sample Size Determination and Statistical Methods

A total of 140 patients will be recruited for this study. Sample size calculations (detailed below) and statistical methods to detect significant changes in the outcome measures were derived from our previous studies evaluating the effects of silicone hydrogel lens wear on the corneal epithelium (Ladage et al, *Ophthalmology* 2001; 108: 1279-1288 and Robertson et al, *IOVS* 2008; 49: 7-15). The magnitude of change for of all outcome measures will be simultaneously compared between lens types using a Type I error rate of $\alpha=0.05$. Statistical analysis will be completed in the Department of Clinical Sciences and Biostatistics at UTSWMC.

A. Surface epithelial cell desquamation

Surface epithelial cell desquamation is the most sensitive and reliable predictor of epithelial perturbation in response to contact lens wear. In our prior studies, silicone hydrogel lens wear worn in a daily modality reduced corneal surface epithelial cell desquamation by 40-50%. We hypothesize that the impact on epithelial shedding rate (cells/minute) will be less following wear of the Dailies Total 1 ($\Delta \leq 20\%$ reduction) compared to wear of a standard silicone hydrogel daily disposable, the ACUVUE TruEye ($\Delta \geq 40\%$ reduction). Assuming a difference in means between the two test lenses of 16.3 cells/minute and a standard deviation of 37 cells/minute, a total sample of 84 subjects in a 2x2 cross-over design will have 80% power at a significance level of $\alpha=0.05$.

B. Drop outs

Additional subjects were added to compensate for the potential dropouts to satisfy the requirements for completion of the 6 month study. Based upon our previous clinical trials, we anticipate a dropout rate of 10-12%. In the absence of time, cost, and ethical concerns, Guo et al. (2013) suggested choosing the largest sample size to guarantee power for all 2 tests. Therefore, we will recruit a total of 94 subjects for this cross-over trial. That is, 47 subjects will be allocated to each sequence in this 2x2 cross-over trial.

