6.4 Data Analysis Procedures

Data analysis will begin with the extraction of data from the master database in ophthalmology. Range and validity checks and determination of validity of missing values will be a first step in analysis. Patient confidentiality will be assumed during data analysis in that the patient names will not be used but will be numerically coded. Data will be analyzed using an intent-to-treat approach.

Continuous demographic and baseline characteristics will be compared between the DAILIES TOTAL1 and the ACUVUE TruEye using Student's t-tests or Wilcoxon rank sum tests. Categorical demographic and baseline characteristics will be compared between the DAILIES TOTAL1 and the ACUVUE TruEye using Fisher's exact tests or Chi-square tests.

Data analysis will be specific to the objectives outlined below:

1. The primary experimental objective of this study is to characterize the effect of the DAILIES TOTAL1 compared to a control, high oxygen permeable silicone hydrogel daily disposable contact lens, the ACUVUE TruEye, on corneal epithelial cell desquamation. This effect will be assessed using a standardized ocular irrigation technique to measure:
 - a. Rate of desquamation of corneal epithelial cells (cells/min).

In this cross-over trial, treatment effects and carryover effects on the rates of desquamation of corneal epithelial cells (cells/min) will be compared between two treatment groups using Student's t-tests in Rosner (2006), and ANOVA in Chow and Liu (2014). If the p-value is less than $\alpha=0.05$ for surface epithelial cell desquamation, then the surface epithelial cell desquamation is considered significantly different between the two groups.

References:

Rosner B. (2006) Fundamentals of Biostatistics, 6th Edition. Thomson-Brooks/Cole.

Chow S and Liu J. (2014) Design and analysis of clinical trials: concepts and methodologies, 3rd Edition. Wiley.

2. The secondary experimental objective of this study is to evaluate the effect of wear of the DAILIES TOTAL1 on the central corneal epithelium compared to a control, high oxygen permeable silicone hydrogel daily disposable contact lens, the ACUVUE TruEye. This effect will be assessed using IVCN to measure:
 - a. Area of surface epithelial cells within the central cornea (μm^2).

Same analytical methods as described above for the primary endpoint will be used for the analysis of the secondary endpoint.

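### The primary variable is given as a rate in one place and as a change in others, and the SD of 37 is unlabelled; a prespecified baseline-adjusted crossover model would hold the stated power under either reading.

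*Combined protocol and SAP*

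**What the plan says.** The primary variable is described in different ways.

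- Section 2.0 names the measure as "Rate of desquamation of corneal epithelial cells (cells/min", and section 6.4 states that "treatment effects and carryover effects on the rates of desquamation of corneal epithelial cells (cells/min) will be compared between two treatment groups". For the method, 6.4 refers to t-tests and ANOVA in two textbooks.
- The primary hypothesis in 1.2 is about "The magnitude of the reduction in corneal epithelial surface cell exfoliation following wear", compared between lenses.
- Section 3.4.4 states that "The magnitude of change for of all outcome measures will be simultaneously compared between lens types". It gives the hypothesis as percent reductions (at most 20% against at least 40%), then sizes the trial in absolute units: "Assuming a difference in means between the two test lenses of 16.3 cells/minute and a standard deviation of 37 cells/minute", with 84 participants and 80% power.

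Section 3.2 schedules ocular irrigation before each wearing period (Visit 2: "Baseline biological indicators (outcome measures) assessed"; likewise Visit 5) and after it (Visits 4 and 7). Each lens therefore has its own baseline.

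For the secondary endpoint, the hypothesis in 1.2 is "The area of corneal surface epithelial cells will not be increased over baseline following wear" for one lens, with an increase for the other. Section 6.4 says: "Same analytical methods as described above for the primary endpoint will be used for the analysis of the secondary endpoint".

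**The concern.** A test on the rates can mean the 2-month rate or the change in rate, and 6.4 does not say which. Two analysts following it could each report a legitimate but different primary p-value. The rate test gives the period baseline a coefficient of 0 and the change score gives it a coefficient of 1. Neither estimates the coefficient from the data.

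The SD of 37 has the same gap. If it describes one variable and the other is tested, the trial no longer has the power it was sized for, and the loss can be large. If the choice stays open until the data are seen, the 5% error rate is not protected. The secondary endpoint inherits the ambiguity because it takes the primary method.

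**Working it through.** **Inputs.** From 3.4.4: difference 16.3 cells/min, SD 37, N = 84 completers, 80% power, alpha 0.05, 2x2 crossover. Two-sidedness is not stated; it is taken from the wording of 6.4. The correlation r between the within-subject baseline difference and the within-subject 2-month difference is not in the documents, so it is shown over a range. Baseline and 2-month variances are assumed equal, and 16.3 is assumed to apply to both rate and change (equal expected period baselines, no carryover).

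**Step 1: reproduce the plan's figure.** Take 37 as a within-subject, per-period SD. The paired lens difference then has SD 37 × √2 = 52.3. The noncentrality is 16.3 / (52.3/√84) = 2.86, and with 82 df power is 80.6%. The exact N is 83, or 84 when made even for two sequences. If 37 were the SD of the paired difference itself, 43 would be enough. The stated N is therefore sound and implies a within-subject SD, but it cannot show whether that SD is of the rate or of the change.

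**Step 2: variance of the paired lens difference.** Let s be the within-subject SD of the rate.

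- Rate: 2s²
- Change: 2s² + 2s² − 2r(2s²) = 4s²(1 − r)
- Baseline fitted as covariate: 2s²(1 − r²)

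If 37 is the rate SD, s = 37. If 37 is the change SD, s² = 37² / [2(1 − r)]. Rate and change have equal variance when 4(1 − r) = 2, that is at r = 0.5.

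**Step 3: power at N = 84** (noncentral t, 82 df; 81 df for the adjusted model), as rate / change / adjusted.

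| r | 37 = rate SD | 37 = change SD |
|---|---|---|
| 0 | 80.6 / 51.4 / 80.5% | 97.9 / 80.6 / 97.9% |
| 0.3 | 80.6 / 66.4 / 84.1% | 91.6 / 80.6 / 93.8% |
| 0.5 | 80.6 / 80.6 / 90.3% | 80.6 / 80.6 / 90.3% |
| 0.7 | 80.6 / 95.4 / 97.7% | 58.9 / 80.6 / 86.4% |

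Two worked cells:

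- Change tested, 37 = rate SD, r = 0: SD = √(4 × 37²) = 74, noncentrality 16.3 / (74/√84) = 2.02, power 51.4%.
- Rate tested, 37 = change SD, r = 0.7: s² = 1369/0.6 = 2282, SD = √(2 × 2282) = 67.6, noncentrality 2.21, power 58.9%.

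**Step 4: completers needed for 80%** at r = 0, 0.3, 0.5, 0.7.

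| Analysis | 37 = rate SD | 37 = change SD |
|---|---|---|
| Mismatched test | change: 164, 116, 83, 51 | rate: 43, 60, 83, 137 |
| Adjusted | 83, 76, 63, 44 | 43, 55, 63, 71 |

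**Step 5: why the adjusted model has a floor.** An estimated coefficient cannot leave more residual variance than one fixed at 0 or at 1. Whichever label is right, one of those two fixed choices has variance 2 × 37². The adjusted variance is therefore at most 2 × 37², and power is at least 80.5% at any r. This also held with the baseline SD at 0.75 to 2 times the on-lens SD. Simulations with 42 per sequence agree with the table to within about 1 to 1.5 percentage points.

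**Step 6: cost of leaving the choice open.** In simulation under no lens difference, each single test held its level (4.4% to 5.2%). Taking the smaller p-value of the rate and change tests gave a type I error of 8.2% to 9.4% over r = 0 to 0.7.

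**The case against.** A coherent reading exists: 2.0 and 6.4 name what is measured, 3.4.4 names what is compared, and 37 may be the change SD, in which case the change test has its 80.6%. That is possible, but no passage says so, and 6.4 can equally be read as a test of the 2-month rate.

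The strongest point concerns r. It is a correlation of within-subject differences, so stable differences between people cancel. With visits at months 1, 3, 4 and 6 and a serial correlation that decays exponentially, r would lie between about −0.06 and 0.33. In that range the plain rate test has at least 80.6% power under both labels, and simply naming the 2-month rate as primary would remove most of the risk. This stands as an argument about size: the rows at r = 0.5 and 0.7 need more correlation than that model gives. But the model is itself an assumption. Within its range the adjusted analysis still matches or beats both alternatives to within 0.1 point; at r = 0.3 it gives 84.1% against 80.6% for the rate and 66.4% for the change, if 37 is the rate SD.

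Four further points carry some weight.

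- If 37 is a total SD entered conservatively, with positive correlation between periods, true power is higher throughout.
- The 8% to 9% error arises only if someone runs both tests and keeps the better one. The plan does not propose that, but does not exclude it either.
- A comparison between lenses does not by itself test the secondary hypothesis, which is worded as a change within each lens. The plan's own choice to reuse the primary method already has that limit.
- The Visit 5 baseline follows the first lens and could carry a residual effect. A rate analysis avoids this.

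**Conclusion.** The concern holds. The documents do not fix one primary variable, do not give the period baselines a role in the test, and do not label the SD; nothing elsewhere in them settles these points. The percent-reduction wording in 3.4.4 adds a third scale: a 20-point gap equals 16.3 cells/min only at a baseline of 16.3/0.20 = 81.5 cells/min, which is not stated.

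The sample size of 84 is not wrong, and neither single test is invalid. The exposure is a mismatch between the variable powered and the variable tested. Power falls below 80% for r under 0.5 if 37 is the rate SD and change is tested, and for r above 0.5 if 37 is the change SD and rates are tested. A fitted baseline removes that dependence at a worst-case cost of about 0.1 point of power. How much it gains depends on r, which is unknown. This should be corrected, but it does not undermine the trial.

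**What to change.** In 6.4, prespecify one primary analysis: a linear mixed model of the 2-month rate (Visits 4 and 7) with lens, period and sequence as fixed effects and participant as a random effect. Include the same-period baseline rate (Visits 2 and 5) as a covariate, split into the participant's mean baseline and the within-participant deviation from it. Test the lens effect two-sided at 0.05. The baseline must be a fitted covariate; simply subtracting it is the analysis that can fall to 51% power.

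Report the unadjusted comparison as a sensitivity analysis. Use the same model for central cell area, since 6.4 carries the primary method over. Align 1.2 and 3.4.4 to this variable, and state whether 37 is the within-subject SD of the rate or of the change. Naming the variable and labelling the SD are needed even if the sponsor prefers another valid model.

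The cost is wording: no new visit, sample or participant. The model spends one or two degrees of freedom (80.5% against 80.6% at r = 0). If residual first-lens effects at Visit 5 differ by c cells/min between lenses, the adjusted estimate shifts by b × c/2, where b is the baseline coefficient; a change score shifts by c/2. The unadjusted result does not use that baseline, which is why it belongs beside the primary one.

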Appendix

A.1 Measurement Procedures

A.1.1 Contact Lens Diary

To ensure compliance, all subjects will be given a contact lens diary at their dispensing visit. Subjects will be asked to record the time of lens insertion and the time of lens removal daily.

A.1.2 Tear Collection

Procedure - all samples are collected from both eyes of human subjects after lens removal by a single, trained investigator. Tear collection will be performed as the first clinical test immediately following lens removal.

- 1) A special fire-polished capillary glass tube is used (Drummond Microcaps)
- 2) The subject's chin is placed comfortably in the chin rest of a Haig-Streit slit lamp under normal illumination.
- 3) The top of the capillary tube is applied to the temporal edge of the tear meniscus inferiorly.
- 4) Three microliters of tears will be collected without touching the lid, conjunctiva or cornea to avoid stimulating reflex tearing from each eye.
- 5) Right and left eye samples will be pooled in a DNase-free microcentrifuge tube. Similarly, DNA extracted from the right and left worn lenses will be pooled.
- 6) All tear samples will be collected by a single trained investigator, numerically coded at time of collection and masked to laboratory personnel.
- 7) Samples will be frozen at -80°C until use.
- 8) Total DNA levels in tear sample volumes taken from each pooled sample will be assessed using the PicoGreen ds DNA assay (Invitrogen, Carlsbad, CA).

A.1.3 Lid Wiper Staining

Fluorescein and lissamine green staining will be used to assess the upper and lower lid wiper in the left eye of all subjects after lens removal.

- 1) 2% unpreserved fluorescein and 1% lissamine green will be sequentially instilled onto the inferior palpebral conjunctiva of the left eye.
- 2) Three minutes following dye instillation, the upper eye lid will be everted using a cotton tipped applicator and LWE staining evaluated.
- 3) Fluorescein staining will be visualized using Cobalt blue illumination and a Wratten No. 12 filter (Kodak, USA). Lissamine green staining will be illuminated using white light. Staining will be imaged using a SONY digital camera mounted to the slit lamp.
- 4) Staining will be graded according to the horizontal linear area (length) and the sagittal height (width) as published by Korb et al, *Cornea* 2010. The individual grades for length and width will be averaged to a final grade for fluorescein and a final grade for lissamine green. The higher of the final fluorescein and lissamine green staining grades were used as the LWE severity according to the following scale:

Grade 0 = no LWE

Grade 1 = mild LWE, score of 0.25 – 1.0

Grade 2 = moderate LWE, score of 1.25 – 2.0

Grade 3 = severe LWE, score of 2.25 – 3.0

b. Severity: Grade 0 = absent; Grade 1 = mild; Grade 2 = moderate; Grade 3 = severe
Fluorescein and lissamine green staining will be used to assess the upper and lower lid wiper in

A.1.4 *In Vivo* Confocal Microscopy

In vivo confocal microscopy will be performed on left eyes after lens removal.

- 1) 1 drop of topical anesthetic (tetracaine) is placed in the lower cul-de-sac of the right and left eyes.
- 2) The patient is seated such that the head is comfortably placed in the microscope chin-forehead rest with no hypo-hyper neck extension, both feet are flat on the floor and both arms are allowed to rest on the microscope table.
- 3) The patient fixates on the wall (distance) or near (light) target with the right eye to provide good fixational acuity.
- 4) One drop of Genteal (Alcon Laboratories, Ft. Worth, TX) is placed on the applanating tip to couple the cornea to the objective. The microscope joystick is used to adjust the microscope in the x-y-z direction to ensure proper alignment on the central cornea.
- 5) The remote controller is used to scan through the full thickness cornea. Images will be acquired by live streaming during scanning. For assessments of limbal changes, including the presence of dendritic cells, the limbal epithelia will be applanated at approximately 3 o'clock position. Patients will be instructed to change their direction of gaze to facilitate imaging. Similar methodology will be used for the lid margin, with eversion of the upper eyelid required. Scanning of the lid margin will be performed using sequential image capture of overlapping regions corresponding to the 5 o'clock position of the limbus to the 7 o'clock position.
- 7) Note that the patient can freely withdraw backwards at any time desired.
- 8) When enough good quality images have been obtained, the patient withdraws the head, and microscopy is terminated.
- 10) For measurements of surface epithelial cell size, cell borders will be manually delineated on screen using MetaMorph software and total area per cell determined.
- 11) Dendritic cells present in the limbus will be manually counted from 3D image stacks using MetaMorph software.

A.1.6 Exfoliated Cell Collection and Quantitation

Ocular irrigation will be performed on the left eyes after lens removal and after staining with fluorescein.

- 1) The patient will be seated with forehead resting against a headrest; a fixation target is placed to orient the eye to be irrigated downwards.

- 2) The irrigating tip is positioned 2 mm below the corneal apex.
- 3) Irrigation involves the delivery of 9 ml of sterile saline to the central cornea for a period of 1 minute via a tubing pump (Cole-Parmer Instrument Co., Chicago, IL).
- 4) Following irrigation, samples will be immediately fixed in 4% paraformaldehyde. This will be accomplished by adding 9 ml of 8% paraformaldehyde (Electron Microscopy Services) to the existing 9 ml of sterile saline containing exfoliated cells.
- 5) Samples will be mixed by gentle inversion and placed on ice until taken to the laboratory for analysis.
- 6) The fixed cell suspension will be passed through a syringe filter holder containing a 13 mm diameter, 5 μ m pore size polycarbonate filter (Nucleopore) to collect cells.
- 7) Each filter is then washed and simultaneously stained by passing 10 ml of sterile physiological saline (0.9% NaCl, pH 7.2) containing 10^{-4} M acridine orange (Sigma) through the filter system.
- 8) After removal from the syringe holder, the filters are placed on microscope slides, allowed to air dry and heated to 80°C in an oven for 10 minutes; each filter is then re-cooled and restained by addition of 1 drop of 10^{-4} M acridine orange solution.
- 9) A Leica inverted fluorescent microscope (Heidelberg, Germany) with an epifluorescence attachment (510 nm dichroic mirror, 450-490 nm excitation filter; 520 nm barrier filter) is used to examine each tissue sample at 1000x magnification under oil immersion.
- 10) The total number of corneal epithelial cells on each filter is recorded. Note: direct visualization of all cells by fluorescence microscopy is required to eliminate any skin cells or other debris contaminants from the final data set.

A.2 FDA Slit Lamp Findings Classification Scales

FDA guideline: Premarket notification 510(k) Guidance Document for Daily Wear Contact Lenses, May 1994, page 64

A.2.1 Edema

Classification		Edema
0	None	No edema
1	Trace	Slight localized or generalized edema a. Dull glass appearance (slightly hazy appearance) of the corneal epithelium, OR b. Just detectable central corneal clouding (CCC) without distinct borders
2	Mild	Mild localized or generalized edema a. Less than 15 vacuoles (microcystic), OR b. Light density CCC. Borders distinct but visible only against pupil, OR c. Corneal striae (1 or more)
3	Moderate	Significant localized or generalized edema a. 15 - 50 vacuoles (microcysts), OR b. Very distinct borders on CCC, OR c. Multiple striae including folds in Descemet's membrane (black lines).
4	Severe	Advanced localized or generalized edema a. More than 50 vacuoles (microcysts) b. Epithelial bullae c. Epithelial sloughing

A.2.2 Corneal Neovascularization

Classification		Vascularization
0	None	No vascular changes
1	Trace	Congestion and dilation of the limbal vessels Single vessel extension <1.5 mm from the prefitting position
2	Mild	Extension of vessels < 1.5 mm from the prefitting position
3	Moderate	Extension of limbal vessels 1.5 to 2.5 mm from the prefitting position
4	Severe	Segmented or circumscribed extensions of limbal vessels more than 2.5 mm inside the limbus, OR extension to within 3.0 mm of corneal apex.
Location (optional):		
N	Nasal	T Temporal
I	Inferior	S Superior
C	Circumferential	X Other (describe)

A.2.3 Corneal Staining

Classification		Corneal Staining
0	None	No staining
1	Trace	Minimal superficial staining or stippling 
 a. Central or generalized b. Peripheral including 3 - 9 o'clock staining, OR c. Dimpling associated with bubbles under lens, OR d. Trace superficial lens insertion marks or foreign body tracks
2	Mild	Regional or diffuse punctate staining 
 a. Central or generalized, OR b. Peripheral including 3 - 9 o'clock staining, OR c. Mild abrasion or foreign body tracks
3	Moderate	Significant dense coalescent staining, corneal abrasion or foreign body tracks
4	Severe	Severe abrasions (greater than 2 mm diameter ¹), ulcerations, epithelial loss, or full thickness abrasion. Diagram and explain

A.2.4 Injection

Classification		Injection
0	None	No injection present
1	Trace	Slight limbal (mild segmented), bulbar (mild regional), and/or palpebral injection
2	Mild	Mild limbal (mild circumcorneal), bulbar (mild diffuse), and/or palpebral injection
3	Moderate	Significant limbal (marked segmented), bulbar (marked regional or diffuse), or palpebral injection
4	Severe	Severe limbal (marked circumcorneal), bulbar (diffuse episcleral or scleral), or palpebral injection

A.2.5 Tarsal Abnormalities

Classification		Tarsal Abnormalities
0	None	Uniform satin appearance of conjunctiva
1	Trace	Slight conjunctival injection without texture
2	Mild	Mild or scattered papillae/follicles <1.0 mm in diameter
3	Moderate	Significant papillae/follicles <1.0 mm in diameter, and/or conjunctival injection
4	Severe	Localized or generalized papillae/follicles >1.0 mm in diameter with or without marked injection

A.2.6 Other (List all reports by specific finding and grade by severity)

Examples include but are not limited to:

Classification		Tarsal Abnormalities
0	None	No other significant biomicroscopic findings
1	Trace	Minimal findings such as a tear film abnormality (debris or low tear break up time)
2	Mild	Mild findings such as: 
 a. Few faint infiltrates b. Lens adhesion
3	Moderate	Significant findings such as: 
 a. Infiltrates (multiple or dense) b. Iritis with minimal cells or flare c. Conjunctivitis or EKC
4	Severe	Severe findings such as: 
 a. Marked infiltrates with overlying staining b. Iritis with marked cells and/or flare c. Corneal or conjunctival infection d. Corneal ulcer e. Recurrent erosion

A.3 Patient Instructions

ACTIONS AND INDICATIONS

Contact lenses are used for the correction of blurred vision due to light being out of focus in non-diseased and otherwise healthy eyes.

STUDY PARTICIPANT GENERAL DIRECTIONS

- Please read and understand all the warnings, daily checks, precautions, contra-indications and adverse reactions sections.
- Do not wear any other lenses and use only the solutions provided by your eye care practitioner specifically for this study.
- It is important that you attend all scheduled office visits and wear your lenses as prescribed.

LENS WEARING SCHEDULE

- Lenses will be worn only during waking hours. Non-preserved saline, provided by your eye care practitioner, may be used to rinse lenses prior to insertion. Upon removal, lenses will be stored in the appropriate vials until your next scheduled appointment. At no time will lenses be left in overnight or re-used on additional days.

WARNINGS

